3. **Research Plan:** Summarize the study design and research procedures using non-technical language that can be readily understood by someone outside the discipline. Be sure to distinguish between standard of care vs. research procedures when applicable, and include any flowcharts of visits specifying their individual times and lengths. Describe the setting in which the research will take place.

The purpose of this study is to evaluate a new treatment option for the management of primary papillary thyroid microcarcinoma (PTMC). Patients referred to Yale Endocrine Surgery for management of cytology-proven PTMC (PTC measuring 1 cm or less in diameter) will be offered inclusion into the study. (See page 24 for specific exclusion criteria.) After enrollment, patients will be assigned to percutaneous ethanol ablation (PEA) of the primary PTMC. Importantly, PEA will not be offered to patients outside of inclusion in the study.

After informed consent is obtained, baseline evaluation includes the following tests:

- a) Baseline ultrasound assessment to confirm size and location of PTMC
- b) Baseline laryngoscopy before initiation of treatment
- c) Baseline quality of life assessment (“SF-36”; Appendix 1)
- d) Baseline pain assessment (“Brief Pain Inventory”, BPI; Appendix 2)
- e) Baseline voice assessment (“Voice Handicap Index”, VHI; Appendix 3)
- f) Baseline symptom assessment (“Thyroid Symptom Questionnaire”, TSQ; Appendix 4)

The SF-36 is a set of easily-administered quality-of-life measures and is a validated tool to evaluate patient quality of life [40-42]. The VHI is an established tool used to assess voice after an intervention [43-45]. The BPI is a simple, well-accepted instrument for the objective assessment of pain [46-48]. The TSQ is a 12-item based questionnaire assessing specific thyroid related symptoms.

Therapy

a. Percutaneous ethanol ablation

Patients in the PEA group will constitute the sole treatment group of the study. These patients will be scheduled for an outpatient procedure with [name] from Interventional Radiology. The volume of 99% ethanol to be injected is calculated using a standardized formula (Ethanol Volume= length × width × height × π / 6) and instilled with a 3-4 cm long 22-25-gauge needle under ultrasound-guidance after administration of local anesthesia. If the patient cannot tolerate the procedure despite adequate local anesthesia, they will be offered conscious sedation. Conscious sedation is a combination of medicines to help you relax (a sedative) and to block pain (an anesthetic) during a medical. You will probably stay awake but may not be able to speak.

It is usually safe, however, overmedication could result in respiratory depression. The patient will be monitored carefully during the entire procedure and the appropriate equipment will be employed if needed.

The procedure itself usually takes only about 60-90 minutes and the patient will be observed for 2-3 hours in the hospital before discharge home.

All patients will receive a phone call to their home 48 hours after the PEA procedure and will be assessed for pain level and voice quality (BPI and VHI).

Every patient will be scheduled for a post-procedure visit in the endocrine surgery clinic approximately 7 – 14 days after their procedure. The post-procedure clinic visit will include the following assessments:

- a) Evaluation of the wound after the intervention
- b) Follow-up ultrasound assessment
- c) Follow-up laryngoscopy after treatment
- d) Follow-up quality of life assessment (SF-36)
- e) Follow-up pain assessment (BPI)
- f) Follow-up voice assessment (VHI)
- g) Follow-up symptom assessment (TSQ)
- h) Cosmesis assessment (“Patient and Observer Scar Assessment Scale”, POSAS; Appendix 5)

During this clinic visit, a thorough evaluation will be performed of the patient's injection site. An endocrine surgeon will evaluate the injection site during this visit using POSAS, a validated tool for the evaluation of surgical scars [49-52].

Formal cancer restaging for patients will take place every 6 months for the first two years and then annually for the following 3 years. These clinic visits will include a thorough clinical examination, surveillance ultrasonography of the neck (thyroid bed, central and bilateral lateral neck lymph nodes), laboratory tests (TSH, free T4, Tg, TgAb), quality of life assessment, pain assessment, voice assessment, symptom assessment, and cosmesis assessment.

Disease progression based on radiographic images utilizing the RECIST (Response Evaluation Criteria in Solid Tumors) criteria will result in recommendation to patient for total thyroidectomy. Disease progression is defined by $\geq 20\%$ increase of diameter of any residual visible tumor, a $\geq 5\text{mm}$ absolute increase in size of any residual visible tumor, appearance of new metastasis to central or lateral neck lymph nodes by ultrasound and FNA biopsy, or appearance of new distant metastases [53].

Duration of Project and Follow Up

Patients will be recruited over 3 years and followed for 5 years after the procedure. After initial treatment, patients will be followed every 6 months for the first two years, and then annually for the next 3 years. The data will be analyzed on an annual basis.

References:

1. Miccoli, P., et al., The impact of thyroidectomy on psychiatric symptoms and quality of life. *J Endocrinol Invest*, 2007. 30(10): p. 853-9.
2. Adler, J.T., et al., Preserving function and quality of life after thyroid and parathyroid surgery. *Lancet Oncol*, 2008. 9(11): p. 1069-75.
3. Weber, T., et al., Effect of parathyroidectomy on quality of life and neuropsychological symptoms in primary hyperparathyroidism. *World J Surg*, 2007. 31(6): p. 1202-9.
4. Cohen, S.M., et al., Creation and validation of the Singing Voice Handicap Index. *Ann Otol Rhinol Laryngol*, 2007. 116(6): p. 402-6.
5. Jacobson, B.H., The Voice Handicap Index (VHI): Development and Validation. *American Journal of Speech-Language Pathology*, 1997. 6: p. 66-70.
6. Jung, S.P., et al., A New Subfascial Approach in Open Thyroidectomy: Efficacy for Postoperative Voice, Sensory, and Swallowing Symptoms. A Randomized Controlled Study. *Ann Surg Oncol*, 2013.
7. Keller, S., et al., Validity of the brief pain inventory for use in documenting the outcomes of patients with noncancer pain. *Clin J Pain*, 2004. 20(5): p. 309-18.

The Yale Endocrine Surgery program is the largest provider of surgical care for patients with endocrine disorders in the State of Connecticut. Yale Endocrine Surgery serves as both a

primary treatment site and a tertiary referral center for patients from surrounding counties and neighboring states. Statistics describing the demographic distribution of the population seeking care by endocrine surgeons are incomplete at this time, but as we begin enrollment into our studies, we anticipate that will be able to compile and update descriptive statistics on the demographics of our population. In this capacity, we will be able to compare the demographic distribution of patients enrolled to the county-level statistics.

6. **Subject classification:** Check off all classifications of subjects that will be specifically recruited for enrollment in the research project. Will subjects who may require additional safeguards or other considerations be enrolled in the study? If so, identify the population of subjects requiring special safeguards and provide a justification for their involvement.

None. All patients referred to Yale Endocrine Surgery who meet inclusion criteria and do not meet exclusion criteria will be offered enrollment into the study. It is possible that the study will eventually include patients who also incidentally belong to one of the following classifications, but no attempt will be made to specifically enroll patients from a particular vulnerable population.

 Children	 Healthy	 Fetal material, placenta, or dead fetus
 Non-English Speaking	 Prisoners	 Economically disadvantaged persons
 Decisionally Impaired	 Employees	 Pregnant women and/or fetuses
 Yale Students	 Females of childbearing potential	

NOTE: Is this research proposal designed to enroll children who are wards of the state as potential subjects? Yes No (If yes, see Instructions section VII #4 for further requirements)

7. **Inclusion/Exclusion Criteria:** What are the criteria used to determine subject inclusion or exclusion?

Inclusion Criteria:

1. Age 18 years and older
2. Diagnosis: single, cytology-proven papillary thyroid carcinoma measuring 1 cm or less in diameter (microcarcinoma, T1a), without visible extrathyroidal extension, and with negative central and lateral neck lymph nodes by ultrasound

Exclusion criteria:

1. Patient refusal to participate
2. History of prior thyroid or parathyroid surgery
3. History of prior recurrent laryngeal nerve injury
4. Inability to make decisions or comply with follow up
5. Co-existing indication for thyroidectomy
6. Aggressive cytologic or molecular features
7. Multifocal papillary thyroid carcinoma
8. Pregnant or breast-feeding
9. Anatomically unfavorable location of the tumor (proximity to recurrent laryngeal nerve or trachea)

10. Documented or suspected distant metastasis
11. History of prior radiation to neck or face
12. Family history of pathological thyroid cancer

Points of Clarification

1. Presence of BRAF V600E mutation is not automatic exclusion
2. Co-existing benign thyroid condition is not automatic exclusion
3. Family history of incidentally identified, asymptomatic, papillary microcarcinoma is not automatic exclusion

8. How will **eligibility** be determined, and by whom?

All patients referred to Yale Endocrine Surgery who meet eligibility criteria and do not meet exclusion criteria will be offered enrollment in the study. The attending endocrine surgeon (Drs. [name], [name], [name] or [name]) will determine eligibility at the time of the initial clinic visit.

9. **Risks:** Describe the reasonably foreseeable risks, including risks to subject privacy, discomforts, or inconveniences associated with subjects participating in the research.

According to the literature, percutaneous ethanol ablation of a thyroid lesion is generally well tolerated. A common adverse effect is transient pain at the injection site. Additional transient adverse effects include dysphonia in 3.9%, worsening of thyrotoxicosis in 1.1%, self-limited fever in 5% and hematoma in 1.8% [37, 39]. There exists a single case report from Germany describing severe ethyl toxic necrosis of the larynx and overlying skin in a patient who previously underwent ethanol instillation as a treatment for an autonomously functioning thyroid nodule (AFTN). The patient almost immediately developed aphonia and severe odynophagia, and was admitted to the hospital for eleven days. Topical ointment, intravenous and inhaled steroids, and intravenous antibiotics were administered. The patient did not require invasive therapy in the acute setting, and the voice returned to near normal within 2 weeks. Follow-up ultrasound several months after the procedure demonstrated that the target nodule was essentially unchanged, suggesting that the majority of the instilled ethanol was actually injected into the subcutaneous tissue and larynx instead of into the thyroid. Six months after the initial procedure, follow-up laryngoscopy demonstrated that a right false vocal fold cyst had developed; this was successfully resected endoscopically ten months after the initial procedure [30]. Finally, there is a risk of recurrence or progression of the PTMC. If follow-up ultrasound examinations demonstrate recurrence or progression, patients will be offered thyroidectomy as standard-of-care treatment.

There exist non-physical risks with this type of study. One of these is the potential loss of privacy. In order to ensure confidentiality within the study, patients are assigned unique identifiers. All electronic data files for this study will either be stored as password-protected files on the secure Yale ITS server or in the Yale Clinical Trials Management System

(OnCore). OnCore is accessed through Yale-networked computers and access is granted only to appropriate study personnel. Any files that contain protected health information will be maintained separately from the rest of other data files and only on the secure server or in OnCore. Ability to access the files is restricted to study investigators.

References:

1. Christou, N. and M. Mathonnet, Complications after total thyroidectomy. *J Visc Surg*, 2013.

The principal investigator or the Human Investigation Committee (HIC) have the authority to stop or suspend the study or require modifications. This protocol presents greater than minimal risks to the subjects. The offered treatment modalities are considered routine in the course of standard clinical care. Although highly unexpected, serious unanticipated and related adverse events or unanticipated problems involving risks to subjects or others will be reported in writing within 5 days to the HIC (using the appropriate forms on the website) and the Department of Surgery. The principal investigator will apprise fellow investigators and study personnel of all adverse events that occur during the conduct of the research project during regular study meetings and e-mails when urgent, as these events are reviewed by the principal investigator.

The principal investigator will assess study data on a continuing basis. All individuals will be recruited without bias for ethnicity, race, gender or age. Any identifying information will remain confidential. All electronic data files for this study will either be stored as password-protected files on an encrypted, password-protected computer, in the Yale Clinical Trials Management System (OnCore), or on the secure Yale ITS server. OnCore is accessed through Yale-networked computers and access is granted only to appropriate study personnel. Any files that contain protected health information will be maintained separately from the rest of other data files and only on the secure server or in OnCore. The research team will only give this coded information to others to carry out this research study. We do not anticipate any adverse events with regard to safety. Should anything unexpected occur, we will comply with current HIC reporting requirements. We will complete annual reports to the HIC about study progress.

There is a theoretical risk that percutaneous ethanol ablation may not work and the microcarcinoma may progress.

Since it is not possible to predict with certainty the absolute risk in any given individual or in advance of first-hand experience with the proposed study methods, we provide a plan for monitoring the data and safety of the proposed study as follows:

The principal investigator will report the following types of events to the IRB:

- a) Adverse events that are serious or life-threatening
 - a. Unanticipated (or anticipated but occurring with a greater frequency than expected)
 - b. Possibly, probably, or definitely related to the drug/device/intervention; and
- b) Other unanticipated problems involving risks to subjects or others.

Moderate Risk DSMP**1. Personnel responsible for the safety review and its frequency:**

The principal investigator will be responsible for monitoring the data, assuring protocol compliance, and conducting the safety reviews at the specified frequency, which must be conducted at a minimum of every 6 months (including when reapproval of the protocol is sought). During the review process, the principal investigator (monitor) will evaluate whether the study should continue unchanged, require modification/amendment, or close to enrollment. Either the principal investigator, the IRB or Yale Cancer Center Data and Safety Monitoring Committee (DSMC) have the authority to stop or suspend the study or require modifications.

2. The risks associated with the current study are deemed moderate for the following reasons:
(choose those that apply)

1. We do not view the risks associated with the percutaneous ethanol injection for PTMC as minimal.
2. Given the now established safety and validity of percutaneous ethanol ablation in the current literature for benign thyroid lesions, we do not view the proposed studies as high risk.

Although we have assessed the proposed study as one of moderate risk, the potential exists for anticipated and/or unanticipated adverse events, serious or otherwise, to occur since it is not possible to predict with certainty the absolute risk in any given individual or in advance of first-hand experience with the proposed study methods. Therefore we provide a plan for monitoring the data and safety of the proposed study as follows:

3. Attribution of Adverse Events:

Adverse events will be monitored for each subject participating in the study and attributed to the study procedures / design by the principal investigator [name] according to the following categories:

- a.) Definite: Adverse event is clearly related to investigational procedure(s)/agent(s).
- b.) Probably: Adverse event is likely related to investigational procedure(s)/agent(s).
- c.) Possible: Adverse event may be related to investigational procedure(s)/agent(s).
- d.) Unlikely: Adverse event is likely not to be related to the investigational procedure(s)/agent(s).
- e.) Unrelated: Adverse event is clearly not related to investigational procedure(s)/agent(s).

4. Plan for Grading Adverse Events:

The following scale will be used in grading the severity of adverse events noted during the study:

1. Mild adverse event
2. Moderate adverse event
3. Severe

5. Plan for Determining Seriousness of Adverse Events:**Serious Adverse Events:**

In addition to grading the adverse event, the PI will determine whether the adverse event meets the criteria for a Serious Adverse Event (SAE). An adverse event is considered serious if it:

1. Is life-threatening OR
2. results in in-patient hospitalization or prolongation of existing hospitalization OR

3. Results in persistent or significant disability or incapacity OR
4. results in a congenital anomaly or birth defect OR
5. Results in death OR
6. based upon appropriate medical judgment, may jeopardize the subject's health and may require medical or surgical intervention to prevent one of the other outcomes listed in this definition, OR
7. Adversely affects the risk/benefit ratio of the study

An adverse event may be graded as severe but still not meet the criteria for a Serious Adverse Event. Similarly, an adverse event may be graded as moderate but still meet the criteria for an SAE. It is important for the PI to consider the grade of the event as well as its "seriousness" when determining whether reporting to the IRB is necessary.

6. Plan for reporting Reportable Adverse Events and other unanticipated problems involving risks to subjects or others to the IRB

The principal investigator will report the following types of events to the IRB: a) adverse events that are serious or life-threatening AND unanticipated (or anticipated but occurring with a greater frequency than expected) AND possibly, probably or definitely related to the drug/device/intervention; and b) other unanticipated problems involving risks to subjects or others.

These adverse events or unanticipated problems involving risks to subjects or others will be reported to the IRB in accordance with IRB Policy 710, using the appropriate forms found on the website.

7. Plan for reporting adverse events to co-investigators on the study, as appropriate the protocol's research monitor(s), e.g., industrial sponsor, Yale Cancer Center Data and Safety Monitoring Committee (DSMC), Protocol Review Committee (PRC), DSMBs, study sponsors, funding and regulatory agencies, and regulatory and decision-making bodies.

For the current study, the following individuals, funding, and/or regulatory agencies will be notified (choose those that apply):

All Co-Investigators listed on the protocol.
Yale Cancer Center Data and Safety Monitoring Committee (DSMC)
National Institutes of Health
Food and Drug Administration (Physician-Sponsored IND # _____)
Medical Research Foundation (Grant _____)

The principal investigator [name] will conduct a review of all adverse events upon completion of every study subject. The principal investigator will evaluate the frequency and severity of the adverse events and determine if modifications to the protocol or consent form are required.

12. Statistical Considerations: Describe the statistical analyses that support the study design.

The Yale Center for Analytical Science was consulted to assist with statistics and will contribute to this study ([name]).

The primary aim of this study is to evaluate the effect of PEA on patient-related outcomes. The primary endpoint will be symptom assessment using the Thyroid Symptom Questionnaire (TSQ)

at the patient's 12-month visit. In addition, quality of life assessment (QOL) using SF36, pain assessment using BPI and voice assessment using VHI will be performed.

A secondary aim of this study is to evaluate the safety and feasibility of using PEA to treat primary PTMC. Consequently, we will monitor potential adverse events at the first clinic visit, including dysphonia, thyrotoxicosis, fever, hematoma, and skin necrosis. By analyzing these variables, the study team hopes to evaluate the safety and feasibility of this treatment modality.

Given the excellent prognosis of patients with PTMC (100% 5-yr survival), we do not expect any death events, progression, and recurrence related to the procedure in a feasible follow-up period. Therefore, the oncologic outcomes, including disease-free interval and overall survival (up to 5-yr follow-up), will be collected but will only serve as exploratory endpoints, evaluated at 5-year follow-up.

Descriptive statistics, including mean and standard deviation for continuous variables and frequency and percentage for categorical variables, will be used to summarize patient characteristics. The adverse events will be investigated in order to assess the safety of the new procedure. The primary analysis will be comparing the pre-operative TSQ score to the post-operative TSQ score. Using standard deviation of 6.38 as reported in the DEPTH (DEPression and THyroid) study [54], the sample size of 16 achieves 90% power to detect a difference of 5.65 between pre- and post-PEA with a type I error of 0.05 using a paired t-test. This effect size is equivalent to one-level difference in responses for 6 items (such as from "Much worse" to "Little worse"), or three-level differences in responses for 2 items (such as from "Much worse" to "Much better"), etc.

Similarly, a power analysis was performed for QOL. The Physical Component and Mental Component of SF-36 will be used. The standard deviations, 9.7 and 11.0 for patients with thyroid disease, respectively, were used to estimate statistical power. The sample size of 16 in each group achieves 90% power to detect a difference of 8.6 in SF-36 Physical Component summary score and 9.8 in Mental Component summary score between the PEA and thyroidectomy groups with a type I error of 0.05.

Time and motion studies and a cost analysis will also be conducted.

SECTION VI: RESEARCH INVOLVING DRUGS, BIOLOGICS, RADIOTRACERS, PLACEBOS AND DEVICES

If this section (or one of its parts, A or B) is not applicable, state N/A and delete the rest of the section.

A. DRUGS, BIOLOGICS and RADIOTRACERS

1. Identification of Drug, Biologic or Radiotracer: What is (are) the **name(s)** of the drug(s) biologic(s) or radiotracer(s) being used? Identify whether FDA approval has been granted and for what indication(s).

Percutaneous ethanol injection is approved by the FDA and is a well-accepted treatment modality for the management of metastatic thyroid carcinoma to the neck, as well as benign thyroid cysts or autonomic nodules [27, 28, 30-32, 36, 55]. The injection of ethanol has been also used successfully in the cure of liver tumors [56-61].

1. Hay, I.D. and J.W. Charboneau, The coming of age of ultrasound-guided percutaneous ethanol ablation of selected neck nodal metastases in well-differentiated thyroid carcinoma. *J Clin Endocrinol Metab*, 2011. 96(9): p. 2717-20.

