- a. What is the Investigational New Drug (IND) **number** assigned by the FDA?
- b. Who holds the IND?
- c. All protocols which utilize a radiotracer not approved by, but regulated by the FDA must provide the IND number: _____

Alternatively, use of the investigational radiotracer may be under RDRC/RSC oversight: (check if appropriate) _____

For all investigational radiotracers, attach a copy of the RDRC/RSC application (for radioisotopes used in the PET Center, PET Center personnel may complete this step)

Go to <http://rsc.med.yale.edu/login.asp?url=myApps.asp>. When you have logged in, complete the application and attach a copy to this submission. NOT APPLICABLE

Alternatively, an **exemption from IND filing requirements** may be sought for a clinical investigation of a drug product that is lawfully marketed in the United States. If there is no IND and an exemption is being sought, review the following categories and complete the category that applies (*and delete the inapplicable categories*): NOT APPLICABLE

2. **Background Information:** Provide a description of previous human use, known risks, and data addressing dosage(s), interval(s), route(s) of administration, and any other factors that might influence risks. If this is the first time this drug is being administered to humans, include relevant data on animal models.

Percutaneous ethanol injection is approved by the FDA and is a well-accepted treatment modality for the management of metastatic thyroid cancer in the neck, as well as benign thyroid cysts or nodules. Ethanol (99%) is injected through the skin into the thyroid tissue under ultrasound guidance and it has been reported in the literature that 0.1 to 1.0 cc ethanol is sufficient for the successful ablation of a PTMC [27, 28, 30-32, 36, 55]. The actual volume of ethanol to be instilled into a particular tumor will be calculated through a standard formula (Ethanol Volume= length × width × height × π / 6). Based on our experience and the existing literature, we believe that most PTMCs will be completely treated with a single procedure, given the small size of the tumors (≤ 1 cm). However, if follow-up ultrasound demonstrates residual tumor after initial treatment, re-treatment will be permitted.

1. Howlader, N.N., AM, *SEER cancer Statistics Review*. 2013.
2. Pacini, F., *Management of papillary thyroid microcarcinoma: primum non nocere!* J Clin Endocrinol Metab, 2013. 98(4): p. 1391-3.

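### Section 12 ties the safety evaluation to the first clinic visit and does not say that later adverse events, which the monitoring plan already records, count towards it.

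*Combined protocol and SAP*

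**What the plan says.** Section V, item 12 (Statistical Considerations) introduces the safety aim and then says: "we will monitor potential adverse events at the first clinic visit, including dysphonia, thyrotoxicosis, fever, hematoma, and skin necrosis". It goes on: "By analyzing these variables, the study team hopes to evaluate the safety and feasibility of this treatment modality". Later the same item adds a general sentence: "The adverse events will be investigated in order to assess the safety of the new procedure". It gives no window, data source, denominator or rule for repeat procedures.

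The Research Plan (Section V, item 3) schedules a clinic visit about 7 to 14 days after the procedure. Section VII, item 5 confirms that the first clinic visit is the one following the procedure. The assessments listed for it include ultrasound, laryngoscopy, and the quality-of-life, pain, voice, symptom and scar instruments, but no blood test. TSH and free T4 are listed for the restaging visits, every six months for two years and then yearly to five years.

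The Data and Safety Monitoring Plan (DSMP; Section V, item 11) is wider. "Adverse events will be monitored for each subject participating in the study", with categories for attribution, severity and seriousness. Safety is reviewed at least every six months. The principal investigator "will conduct a review of all adverse events upon completion of every study subject" and will "evaluate the frequency and severity of the adverse events and determine if modifications to the protocol or consent form are required".

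Section VI, A.2 states that "if follow-up ultrasound demonstrates residual tumor after initial treatment, re-treatment will be permitted".

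**The concern.** Item 12 sets 12 months for the primary symptom score and five years for the oncologic outcomes. For safety the only time it names is a visit one to two weeks after injection, and the safety conclusion is to come from the variables collected there. Anything that appears later, or after a second injection, has no stated place in that analysis.

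This matters because the Background says the procedure has not been used before for primary papillary thyroid cancer, so the trial's own safety rate will be read closely. The Risks section (Section V, item 9) shows that a complication can surface late. In the case report it cites, "Six months after the initial procedure, follow-up laryngoscopy demonstrated that a right false vocal fold cyst had developed", and the cyst was resected at ten months. A first-visit summary would not show that event. A published rate with no stated window could be taken as cumulative when it covers only the first two weeks.

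Thyrotoxicosis raises a narrower question. It is one of the five named events, but it is assigned to a visit for which the Research Plan lists no thyroid function test.

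**Working it through.** **No safety figure to reproduce.** Item 12 gives no sample size, precision or threshold for safety. Its only relevant power figure is 90% for the primary symptom score with 16 patients. A two-sided paired t-test with difference 5.65 and SD 6.38 (taken as the SD of the difference) gives 91.1%, so that figure reproduces, but it does not bear on this point.

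**Texts side by side.**

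| Question | Item 12 | DSMP (item 11) and other sections |
|---|---|---|
| Which events | Five named; the list is left open | All adverse events |
| When | First clinic visit, about day 7 to 14; the general sentence gives no time | Each subject, no time limit; safety review at least six-monthly; all events reviewed at subject completion |
| Attribution and severity | Not mentioned | Five attribution categories, three grades |
| After re-treatment | Not mentioned | Re-treatment permitted (Section VI, A.2); no assessment tied to it by name |
| Thyroid function | Thyrotoxicosis named at the first visit | TSH and free T4 listed at restaging, not at the first visit (item 3) |

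The visit falls in the first 7/(5 × 365.25) = 0.4% to 14/(5 × 365.25) = 0.8% of planned follow-up. This describes the window only. It does not measure what is missed, since the common reactions cited are early and transient.

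**Direction.** Fix the event definition and the denominator n of treated patients. Let a be the number of patients with an event by the first visit and b the number with an event by the 12-month visit. Everyone counted in a is also counted in b, so a/n ≤ b/n. The first-visit rate can equal the cumulative rate or fall below it, but cannot exceed it.

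**Size for one patient.** Inputs are n = 16 (item 12, power statement) and n = 40 (Section VII, item 1, target enrolment). Exact (Clopper-Pearson) 95% limits:

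- 0 events: upper limit = 1 − 0.025^(1/n)
- 1 event: lower limit = 1 − 0.975^(1/n); the upper limit solves (1 − p)^n + n·p·(1 − p)^(n−1) = 0.025

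| n | No event by the first visit | One patient with only a late event |
|---|---|---|
| 16 | 0% (0 to 20.6%) | 6.3% (0.2 to 30.2%) |
| 40 | 0% (0 to 8.8%) | 2.5% (0.1 to 13.2%) |

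These rows assume an event; they do not predict one. The documents give neither a late-event rate nor a re-treatment rate for primary microcarcinoma, so no expected shortfall is calculated.

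**The case against.** The case on the other side is substantial.

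- **The general sentence in item 12 is unrestricted** and may be meant to cover every recorded event. That is a fair reading. But the sentence does not say so, and the only time point in the item points the other way. The supported statement is that item 12 does not say later events count; it does not rule them out.
- **The DSMP review evaluates the frequency and severity of all events**, which is itself a safety evaluation. This stands. A reader might infer that late events go unrecorded or that patients are unprotected, and the documents do not support that. What is missing is a link from the DSMP record to the analysis that answers the safety objective.
- **The visit is defined relative to the procedure**, so the day 7 to 14 check, and the 48-hour call, may recur after a repeat injection. A reader might infer that events after re-treatment are missed. The documents are silent either way, so that cannot be claimed.
- **The case-report patient had immediate symptoms.** This stands: a per-patient count of any event would be unchanged, and the example shows only that a late event can occur. The cyst was found by laryngoscopy, which is not on the restaging list, so the voice and laboratory data there would not show it directly.
- **A cumulative count of all adverse events would mix in other causes.** This also stands. Patients whose disease progresses are recommended thyroidectomy, which carries nerve and parathyroid risks of its own. The endpoint therefore needs an attribution rule, separate reporting after surgery, and a method for incomplete follow-up.
- **Appendix 6 holds the details of the follow-up visits and was not available.** It may list later adverse event checks or a first-visit thyroid test. A reader might infer that thyrotoxicosis cannot be detected at the first visit; that goes further than the text allows.

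**Conclusion.** The point holds as a gap in the analysis plan. Item 12 names the first visit as the only time for the safety evaluation, its general sentence does not extend that window, and it makes no use of the DSMP record. Read literally, the reported rate can equal or understate the rate over follow-up.

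The size is unknown and may be zero. A reader might infer that the trial will materially understate harm, but nothing in the documents supports a number for that. With 16 to 40 patients, each patient with only a late event adds 2.5 to 6.3 percentage points. The firmer harm is to interpretation, because a reader could not tell a two-week rate from a cumulative one. The conclusion rests on the literal wording of item 12 and on the supplied text without Appendix 6. Confidence is medium. The change should be made because it is cheap and answers a stated objective better.

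**What to change.** Reconcile Section V, items 11 and 12, with the re-treatment provision in Section VI, A.2, by adding the following to item 12:

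1. **Endpoint.** Per-patient incidence of DSMP-recorded adverse events rated possibly, probably or definitely related to PEA, among all treated patients, from first injection through the 12-month visit. State that events after any re-treatment count.
2. **Separation.** Report events after any thyroidectomy separately, and list all adverse events regardless of attribution.
3. **Estimation.** Exact 95% confidence intervals at 12 months, and a five-year update by a method that allows for incomplete follow-up.
4. **Early summary.** Keep the first-visit figure, labelled as such; it suits transient events such as fever and hematoma.
5. **Sources.** Use the DSMP record together with the voice, TSH and free T4 data already planned at restaging. Check Appendix 6 for how thyrotoxicosis is ascertained at the first visit, and state it.

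The 12-month window is proposed because it matches the primary endpoint; another window would serve if stated in advance. The cost is a few sentences and one more table, with no added visit or test. The downside is that the cumulative rate may look less favourable than the first-visit rate.
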